6.2 Administration, Supply, and Storage

Nivolumab will be dosed at 480mg IV every 4 weeks (+/- 3 days) beginning on C1D1. Treatment will be administered on an outpatient basis.

PRODUCT INFORMATION TABLE: Please also see Nivolumab Investigator Brochure.

Product Description and Dosage Form	Potency	Primary Packaging (Volume)	Appearance	Storage Conditions (per label)
Nivolumab BMS-936558-01 Solution for Injection	100 mg (10 mg/mL)	10 mL vial	Clear to opalescent colorless to pale yellow liquid. May contain particles.	2 to 8°C. Protect from light and freezing.

*Nivolumab may be labeled as BMS-936558-01 Solution for Injection

If stored in a glass front refrigerator, vials should be stored in the carton. Recommended safety measures for preparation and handling of nivolumab include laboratory coats and gloves.

For additional details on prepared drug storage and use time of nivolumab under room temperature/light and refrigeration, please refer to the BMS-936558 (nivolumab) Investigator Brochure section for “Recommended Storage and Use Conditions”.

7 DOSE ADJUSTMENT AND DELAY, TREATMENT DISCONTINUATION, WITHDRAWAL, AND TERMINATION CRITERIA

7.1 Dosing and Dose Modifications

7.1.1 Dosing

Nivolumab 480mg will administered intravenously every 4 weeks approximately (+/-3 days) over an approximate 30 minute infusion time beginning on C1D1 until progression or end of study.

7.1.2 Dose Modifications

There will be no dose modifications permitted.

7.2 Dose delay and treatment discontinuation

Dose delay criteria apply for all drug-related adverse events .

7.3 Dose Delay Criteria

Nivolumab administration should be delayed for the following:

- Any Grade ≥ 2 non-skin, drug-related adverse event, with the following exceptions:
 - Grade 2 drug-related fatigue or laboratory abnormalities do not require a treatment delay.
- Any Grade 3 skin, drug-related adverse event.
- Any Grade 3 drug-related laboratory abnormality, with the following exceptions for AST, ALT, or total bilirubin:
 - Delay dosing for drug-related AST, ALT, or total bilirubin grade ≥ 2 toxicity.
- Grade 3 amylase or lipase abnormalities that are not associated with symptoms or clinical manifestations of pancreatitis do not require a dose delay.
- Grade 3 lymphopenia does not require a dose delay.
- Any adverse event, laboratory abnormality, or intercurrent illness, which, in the judgment of the investigator, warrants delaying the dose of study medication.

Because of the potential for clinically meaningful nivolumab-related AEs requiring early recognition and prompt intervention, management algorithms have been developed for suspected pulmonary toxicity, GI, hepatotoxicity, endocrinopathy, skin toxicity, neurological toxicity and renal toxicity. The recommendations are to follow the nivolumab IB adverse event algorithm (Appendix A).

7.4 Criteria to Resume Treatment

Missed doses of nivolumab should be administered when subject meets criteria to resume treatment. If a dose has been missed, the subject should wait until the next scheduled dosing date.

Subjects may resume treatment with study drug when the drug-related AE(s) resolve to Grade ≤ 1 or baseline value, with the following exceptions:

- Subjects may resume treatment in the presence of Grade 2 fatigue.
- Subjects who have not experienced a Grade 3 drug-related skin AE may resume treatment in the presence of Grade 2 skin toxicity.
- For subjects with Grade 2 AST, ALT, or total bilirubin elevations, dosing may resume when laboratory values return to baseline and management with corticosteroids, if needed, is complete.
- Subjects with combined Grade 2 AST/ALT **AND** total bilirubin values meeting discontinuation parameters should have treatment permanently discontinued.
- Drug-related diarrhea, or colitis, must have resolved to baseline before treatment is resumed.
- Subjects with persistent Grade 1 pneumonitis after completion of a steroid taper over at least 1 month may be eligible for retreatment if discussed with and approved by the investigator.
- Drug-related endocrinopathies adequately controlled with only physiologic hormone replacement may resume treatment.

If treatment is delayed >10 weeks, the subject must be permanently discontinued from study therapy.

7.5 Discontinuation Criteria

Treatment with nivolumab should be permanently discontinued for any of the following:

- Any Grade 2 drug-related uveitis or eye pain or blurred vision that does not respond to topical therapy and does not improve to Grade 1 severity within the re-treatment period **OR** requires systemic treatment.
- Any Grade 3 non-skin, drug-related adverse event lasting > 7 days, with the following exceptions for drug-related laboratory abnormalities, uveitis, pneumonitis, bronchospasm, diarrhea, colitis, neurologic toxicity, hypersensitivity reactions, and infusion reactions:
 - Grade 3 drug-related uveitis, pneumonitis, bronchospasm, diarrhea, colitis, neurologic toxicity, hypersensitivity reaction, or infusion reaction of any duration requires discontinuation.
 - Grade 3 drug-related endocrinopathies adequately controlled with only physiologic hormone replacement do not require discontinuation, except for Grade 3 adrenal insufficiency which requires permanent discontinuation.
 - Grade 3 drug-related laboratory abnormalities do not require treatment discontinuation except:
 - Grade 3 drug-related thrombocytopenia > 7 days or associated with bleeding requires discontinuation.
 - Any drug-related liver function test (LFT) abnormality that meets the following criteria require discontinuation:

- Grade ≥ 3 drug-related AST, ALT, or total bilirubin requires discontinuation.
 - Concurrent AST or ALT $> 3 \times \text{ULN}$ and total bilirubin $> 2 \times \text{ULN}$.
- Any Grade 4 drug-related adverse event or laboratory abnormality, except for the following events which do not require discontinuation:
 - Grade 4 amylase or lipase abnormalities that are not associated with symptoms or clinical manifestations of pancreatitis.
 - Isolated Grade 4 electrolyte imbalances/abnormalities that are not associated with clinical sequelae and are corrected with supplementation/appropriate management within 72 hours of their onset.
 - Grade 4 neutropenia ≤ 7 days.
 - Grade 4 lymphopenia or leukopenia.
 - Grade 4 drug-related endocrinopathy AEs, such as, hyper- or hypothyroidism, or glucose intolerance, that resolve or are adequately controlled with physiologic hormone replacement (corticosteroids, thyroid hormones) or glucose-controlling agents, respectively, may not require discontinuation after discussion with and approval from the investigator. Grade 4 drug-related adrenal insufficiency or hypophysitis requires discontinuation regardless of control with hormone replacement.
- Any dosing interruption lasting > 10 weeks unless the investigator is consulted and agrees with the rationale for resuming therapy after a delay > 10 weeks. Note that tumor assessments should continue as per protocol even if dosing is interrupted.
- Any adverse event, laboratory abnormality, or intercurrent illness which, in the judgment of the Investigator, presents a substantial clinical risk to the subject with continued nivolumab dosing.

7.6 Treatment of Nivolumab-Related Infusion Reactions

Since nivolumab contain only human immunoglobulin protein sequences, each is unlikely to be immunogenic and induce infusion or hypersensitivity reactions. However, if such a reaction were to occur, it might manifest with fever, chills, rigors, headache, rash, pruritis, arthralgias, hypo- or hypertension, bronchospasm, or other symptoms. Infusion reactions should be graded according to NCI CTCAE v.5.0 guidelines.

Treatment recommendations are provided below and may be modified based on local treatment standards and guidelines as appropriate:

For Grade 1 symptoms: (Mild reaction; infusion interruption not indicated; intervention not indicated)

Remain at bedside and monitor subject until recovery from symptoms. The following prophylactic premedications are recommended for future infusions: diphenhydramine 50 mg (or equivalent) and/or paracetamol 325 to 1000 mg (acetaminophen) at least 30 minutes before additional nivolumab administrations.

For Grade 2 symptoms: (Moderate reaction requires therapy or infusion interruption but responds promptly to symptomatic treatment [e.g. antihistamines, non-steroidal anti-inflammatory drugs, narcotics, corticosteroids, bronchodilators, IV fluids]; prophylactic medications indicated for up to 24 hours).

Stop the nivolumab infusion, begin an IV infusion of normal saline, and treat the subject with diphenhydramine 50 mg IV (or equivalent) and/or paracetamol 325 to 1000 mg

(acetaminophen); remain at bedside and monitor subject until resolution of symptoms. Corticosteroid or bronchodilator therapy may also be administered as appropriate. If the infusion is interrupted, then restart the infusion at 50% of the original infusion rate when symptoms resolve; if no further complications ensue after 30 minutes, the rate may be increased to 100% of the original infusion rate. Monitor subject closely. If symptoms recur then no further nivolumab will be administered at that visit. Administer diphenhydramine 50 mg IV, and remain at bedside and monitor the subject until resolution of symptoms. The amount of study drug infused must be recorded on the electronic case report form (eCRF). The following prophylactic premedications are recommended for future infusions: diphenhydramine 50 mg (or equivalent) and/or paracetamol 325 to 1000 mg (acetaminophen) should be administered at least 30 minutes before additional nivolumab or administrations. If necessary, corticosteroids (recommended dose: up to 25 mg of IV hydrocortisone or equivalent) may be used.

For Grade 3 or Grade 4 symptoms: (Severe reaction, Grade 3: prolonged [i.e. not rapidly responsive to symptomatic medication and/or brief interruption of infusion]; recurrence of symptoms following initial improvement; hospitalization indicated for other clinical sequelae [e.g. renal impairment, pulmonary infiltrates]). Grade 4: (life-threatening; pressor or ventilatory support indicated).

Immediately discontinue infusion of nivolumab. Begin an IV infusion of normal saline, and treat the subject as follows. Recommend bronchodilators, epinephrine 0.2 to 1 mg of a 1:1,000 solution for subcutaneous administration or 0.1 to 0.25 mg of a 1:10,000 solution injected slowly for IV administration, and/or diphenhydramine 50 mg IV with methylprednisolone 100 mg IV (or equivalent), as needed. Subject should be monitored until the investigator is comfortable that the symptoms will not recur. Nivolumab will be permanently discontinued. Investigators should follow their institutional guidelines for the treatment of anaphylaxis. Remain at bedside and monitor subject until recovery from symptoms. In the case of late-occurring hypersensitivity symptoms (e.g. appearance of a localized or generalized pruritis within 1 week after treatment), symptomatic treatment may be given (e.g. oral antihistamine, or corticosteroids).

7.7 Immunotherapy Adverse Event Management

Because of the potential for clinically meaningful nivolumab-related AEs requiring early recognition and prompt intervention, management algorithms have been developed for suspected pulmonary toxicity, GI toxicity, hepatotoxicity, endocrinopathy, skin toxicity, neurological toxicity, and renal toxicity (Nivolumab IB).

These adverse event management algorithms are included in Appendix A.

7.8 Removal of Subjects from the Study, Therapy Assessment

7.8.1 Subject withdrawal

Single subject termination is by definition when the patient is withdrawn or when the patient has died. The study termination page in the eCRF must be completed.

The Investigator also has the right to withdraw subjects from the study in the event of:

- Occurrence of an exclusion criterion, which is clinically relevant and affects the subject's safety, and discontinuation is considered necessary by the Investigator and/or the Sponsor.
- Therapeutic failure requiring urgent additional medication (if applicable)
- Occurrence of AEs, if discontinuation of study medication is considered necessary by the Investigator and/or subject (if applicable).
- Intake of non-permitted concomitant medication as defined in Appendix A where the predefined consequence is withdrawal from the study.
- Progression of disease (subjects will only come off study after meeting PCWG3 criteria for radiographic progression or clinical progression as determined by the treating physician).
- Lack of subject compliance.
- Protocol violation.

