- PSA progression-free survival (PSA-PFS), defined as a time from initiation on nivolumab therapy until PSA increase of 25%, confirmed with another measurement at least 4 weeks later (PCWG3). Patients will be allowed to stay on study until PSA increases 100% (i.e. doubles) from baseline value.
- Metastasis-free survival (PCWG3)
- Undetectable PSA: Defined as a PSA level <0.1 lasting ≥ 12 weeks
- Time to initiation of next systemic therapy

Exploratory Endpoints

- To associate PSA₅₀ response to nivolumab with CD4, CD8, FOXP3, PD-1, PD-L1 levels, MMR and CDK12 mutational status by IHC in archival tumor tissue.
- To associate clinical responses to nivolumab with the expansion of anti-tumor peripheral T cell clones.
- To associate clinical responses to nivolumab with generation of tumor associated antigens as determined by PhIP-seq testing.
- To investigate primary and acquired resistance to PD-1 inhibitor therapy in these biomarker-selected patients (JAK1/2 mutations, B2M expression)

Exploratory Analyses

PD-1, PD-L1, FOXP3, CD4, CD8, MSH2, MSH6, MLH1, PSM2, CDK12 protein levels:

Archival tumor specimens including prostatectomy or needle biopsy of primary tumor, will be analyzed. IHC staining for PD-1 and PD-L1 will be performed and scored as $<1\%$, $1-5\%$, $5-10\%$, $>10\%$ and the results will be associated with responses for both proteins, separately, using descriptive statistics and Fisher's Exact Tests. IHC will be used to quantify the CD4, CD8, and FOXP3 levels. Using analytical microscopy, [name] can quantify the number of T cells per surface area of tumor analyzed. The median number of CD4+ and CD8+ intratumor lymphocytes will be compared in PSA₅₀ responders versus non-responders using a T-test. We will also correlate CD4+ and CD8+ lymphocyte tumor infiltration in patients that obtain an undetectable PSA versus those with progressive disease as best response. Lastly, we will correlate response to nivolumab with MMR and CDK12 mutational status.

Interrogate for tumor-associated neoantigens (TAAs) and mutation-associated neoantigens (MANAs):

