9. CRITERIA FOR OUTCOME ASSESSMENT/THERAPEUTIC RESPONSE

9.1 Outcome Assessment

All baseline evaluations will be performed as closely as possible to the beginning of treatment (within 7 days). For subsequent evaluations, the method of assessment and techniques will be the same as those used at baseline.

- Tumor markers.
PSA measurements will be used to assess the primary endpoint.

9.1.1 *Primary endpoint*

The primary endpoint is defined as a PSA₅₀ response, defined as a $\geq 50\%$ decline in PSA from baseline, confirmed with a second measurement at least 4 weeks later.

9.1.2 *Secondary endpoints*

9.1.2.1. *Safety*

This endpoint is defined as incidence of grade 3-5 toxicities based upon CTCAE v.5.0 standard grading scales.

9.1.2.2. *PSA Progression-Free Survival (PFS)*

PSA progression (PSA progression-free survival; PSA-PFS) will be defined per PCWG3 guidelines.

For those subjects showing an initial decline in PSA from baseline, this is defined as an increase in PSA that is $\geq 25\%$ above the nadir, an absolute increase of $\geq 2\text{ng/ml}$ from nadir, which is confirmed by a second value ≥ 3 weeks later (i.e. a confirmed rising trend).

For those subjects with no decline in PSA from baseline, this is defined as an increase in PSA that is $\geq 25\%$ and an absolute increase of $\geq 2\text{ng/ml}$ after 12 weeks.

Patients will be allowed to stay on study beyond PSA progression, as long as they do not have evidence of radiographic or clinical progression as determined by their treating physician.

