Rule out non-inflammatory causes. If non-inflammatory cause, treat accordingly and continue I-O therapy

Patients on IV steroids may be switched to an equivalent dose of oral corticosteroids (e.g. prednisone) at start of tapering or earlier, once sustained clinical improvement is observed. Lower bioavailability of oral corticosteroids should be taken into account when switching to the equivalent dose of oral corticosteroids.

Pulmonary Adverse Event Management Algorithm

[figure not shown]
Rule out non-inflammatory causes. If non-inflammatory cause, treat accordingly and continue I-O therapy. Evaluate with imaging and pulmonary consultation.

Patients on IV steroids may be switched to an equivalent dose of oral corticosteroids (e.g. prednisone) at start of tapering or earlier, once sustained clinical improvement is observed. Lower bioavailability of oral corticosteroids should be taken into account when switching to the equivalent dose of oral corticosteroids.

Hepatic Adverse Event Management Algorithm

Rule out non-inflammatory causes. If non-inflammatory cause, treat accordingly and continue I-O therapy. Consider imaging for obstruction.

[figure not shown]
Patients on IV steroids may be switched to an equivalent dose of oral corticosteroids (e.g. prednisone) at start of tapering or earlier, once sustained clinical improvement is observed. Lower bioavailability of oral corticosteroids should be taken into account when switching to the equivalent dose of oral corticosteroids.

*I-O therapy may be delayed rather than discontinued if AST/ALT ≤ 8 x ULN and T.bili ≤ 5 x ULN.

**The recommended starting dose for grade 4 hepatitis is 2 mg/kg/day methylprednisolone IV.

Endocrinopathy Management Algorithm

[figure not shown]
Rule out non-inflammatory causes. If non-inflammatory cause, treat accordingly and continue I-O therapy. Consider visual field testing, endocrinology consultation, and imaging.

Patients on IV steroids may be switched to an equivalent dose of oral corticosteroids (e.g. prednisone) at start of tapering or earlier, once sustained clinical improvement is observed. Lower bioavailability of oral corticosteroids should be taken into account when switching to the equivalent dose of oral corticosteroids.

Skin Adverse Event Management Algorithm

Rule out non-inflammatory causes. If non-inflammatory cause, treat accordingly and continue I-O therapy.

[figure not shown]

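### The synopsis and the body of the protocol give different rules for leaving the study on a rising PSA, which changes who is censored; the rules on delays over 10 weeks and on liver toxicity each set a permission against a mandate

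*Combined protocol and SAP*

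**What the plan says.** **Leaving the study on PSA.** The synopsis, under the PSA-PFS secondary endpoint: "Patients will be allowed to stay on study until PSA increases 100% (i.e. doubles) from baseline value". Section 7.8.1, in brackets after the disease-progression reason for withdrawal: "subjects will only come off study after meeting PCWG3 criteria for radiographic progression or clinical progression as determined by the treating physician". Section 9.1.2.2: "Patients will be allowed to stay on study beyond PSA progression, as long as they do not have evidence of radiographic or clinical progression". Section 7.1.1 gives nivolumab "beginning on C1D1 until progression or end of study" and does not say which kind of progression.

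**Delay over 10 weeks.** Section 7.4: "If treatment is delayed >10 weeks, the subject must be permanently discontinued from study therapy". Section 7.5 lists among its reasons for a permanent stop: "Any dosing interruption lasting > 10 weeks unless the investigator is consulted and agrees with the rationale for resuming therapy".

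**Liver.** Section 7.5 has two relevant stopping lines. One is by grade: "Grade ≥ 3 drug-related AST, ALT, or total bilirubin requires discontinuation". The other applies to AST or ALT above 3 x ULN together with total bilirubin above 2 x ULN. The hepatic footnote in Appendix A says: "I-O therapy may be delayed rather than discontinued if AST/ALT ≤ 8 x ULN and T.bili ≤ 5 x ULN". Section 7.3 recommends following Appendix A, section 7.7 only says where the algorithms are, and Appendix A introduces itself as guidance for the investigator.

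**What depends on these rules.** Under 11.1.1 a PSA50 response counts only if it occurs during nivolumab treatment. Sections 11.1.2.2 and 11.1.2.4 censor PSA-PFS and metastasis-free survival at removal from study.

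**The concern.** When an endpoint is censored at removal, the removal rule is part of its definition. Here the plan gives one rule with a PSA ceiling and one without. If men are removed because PSA is rising, and are then censored for an endpoint that measures PSA rising, the censoring is informative. Kaplan-Meier assumes that it is not. The two rules could therefore give different PSA-PFS curves from the same men, and the text does not say which applies.

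The delay and liver conflicts are of another kind. They allow two similar men to be handled differently, with one stopped and the other resumed or held. That matters for safety and for what counts as a protocol deviation. It also matters for how long a man stays in the window in which a PSA50 response can count.

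**Working it through.** **The plan's own figure.** The only design figure is the table of 95% Wilson intervals for n = 15. For 5 responders, with p = 0.333 and z = 1.96, the centre is (0.333 + 3.84/30)/(1 + 3.84/15) = 0.367. The half-width is 1.96 x sqrt(0.2222/15 + 3.84/900)/1.256 = 0.216. This gives 15.2 to 58.3%, as stated. All ten rows reproduce, and this point does not dispute the table.

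**1. PSA doubling against PSA progression.**

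Inputs: entry PSA of at least 1.0 ng/mL (3.1, 3.3); removal at 2 x baseline (synopsis); for men with no decline, PSA progression at a rise of at least 25% and at least 2 ng/mL, after 12 weeks (9.1.2.2).

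For baseline B with no decline, removal is at 2B and progression at max(1.25B, B + 2). Below 8 ng/mL the B + 2 term governs. Doubling then comes first when 2B < B + 2, that is, when B < 2.

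| Baseline (ng/mL) | Doubling | 9.1.2.2 progression | First |
|---|---|---|---|
| 1.0 | 2.0 | 3.0 | doubling |
| 1.5 | 3.0 | 3.5 | doubling |
| 2.0 | 4.0 | 4.0 | tie |
| 3.0 | 6.0 | 5.0 | progression |

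This compares PSA levels only. The 12-week condition can only push progression later.

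After a decline to nadir N (with N below 8), progression is at N + 2, so doubling comes first when N > 2B - 2. At B = 1.0 that is every nadir above 0. At B = 1.5 it needs a nadir above 1.0. At B of 2.0 or more it cannot happen, because the nadir would have to exceed baseline.

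In time, assume steady exponential growth from 1.0 ng/mL. Doubling takes one doubling time, and reaching 3.0 takes ln 3/ln 2 = 1.585 doubling times. For assumed doubling times of 3, 6 and 12 months, the synopsis rule removes and censors at months 3, 6 and 12. Under 7.8.1 and 9.1.2.2 the same men would reach the PSA-PFS level at about months 4.8, 9.5 and 19.0, if still followed.

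Under 11.1.2.2 the event is a 25% rise over nadir with no absolute minimum. Since 1.25N is at most 1.25B, which is below 2B, the event level is reached before doubling. The removal rule then hardly touches PSA-PFS.

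**2. Metastasis-free survival.** On-treatment scans start at C7D1 (5.2.2), six 4-week cycles after C1D1: 24 weeks, or 24/4.345 = 5.5 months. With no decline and an assumed doubling time under about 5.5 months, a man leaves before that scan under the synopsis rule and stays under 7.8.1. Follow-up is shorter, but he is still imaged: 5.3 and the study calendar require CT and bone scan at the end-of-treatment visit if none was done in the prior month.

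**3. PSA50.** One responder gained or lost in 15 is 1/15 = 6.7 points, for example 5/15 (15.2 to 58.3%) against 6/15 (19.8 to 64.3%). This is the step size, not a prediction that it will occur.

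**4. Delay.** Ten weeks is 70/28 = 2.5 cycles. Beyond it, 7.4 has no exception and 7.5 has one at the investigator's agreement.

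**5. Liver.** The 7.5 concurrent criterion starts above 3 x ULN for AST/ALT with bilirubin above 2 x ULN. The footnote reaches up to 8 x and 5 x ULN. In the overlap, AST/ALT above 3 and up to 8 x ULN with bilirubin above 2 and up to 5 x ULN, 7.5 requires a stop and the footnote permits a delay. The Grade 3 line in 7.5 is not needed for this, and the documents do not express grades as ULN multiples.

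**The case against.** The strongest reply is that the body of the protocol is broadly consistent on progression and the synopsis sentence is the outlier. Section 9.4 lists only radiographic progression, and 7.8.1 and 9.1.2.2 add clinical progression. That is fair. But the synopsis is current text and nothing says the body prevails. A treating physician might also count PSA doubling as clinical progression, which would bring the rules together, but no section says so.

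Several stronger readings are tempting and do not hold.

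- A reader might infer that no site can comply with all these passages. For delay and liver that is wrong: the exception in 7.5 and the footnote are permissions, so a site that stops in every such case breaches nothing. The conflict arises only when a site uses the permission.
- A reader might infer that sites will manage similar men differently. The documents show conflicting permissions, not conduct. With two sites and monthly protocol meetings (10.3), divergence is possible, not shown.
- A reader might infer that all three conflicts shift censoring. They do not. Censoring is at removal from study, whereas the delay and liver rules concern study drug, and 7.5 keeps tumor assessments going during an interruption. Time to next systemic therapy is censored only at consent withdrawal or loss to follow-up.
- A reader might infer that men removed at doubling go unscanned. The end-of-treatment imaging prevents that.
- A reader might treat Appendix A as binding. It calls itself guidance, and its hepatic flow chart is not shown in the text available, so what the footnote attaches to cannot be read.

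On the primary endpoint the effect is also narrow. A man at 200% of baseline must fall by 75% from there to reach 50% of baseline, and any response he had before doubling already counts.

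**Conclusion.** The concern holds in this form. On PSA, the synopsis and sections 7.8.1 and 9.1.2.2 give incompatible end-of-participation rules, and 7.1.1 does not settle how long treatment runs. Under the 9.1.2.2 definition this produces informative censoring of PSA-PFS for men with no decline and a baseline from 1.0 to below 2 ng/mL, all of whom are eligible, and for some men with a decline in that range. Under the 11.1.2.2 definition the PSA-PFS effect is small, but follow-up for metastasis-free survival and the response window could still differ.

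On delays over 10 weeks and on liver values, a permission conflicts with a mandate. The consequence is possible inconsistency in safety management, deviation counting and time on nivolumab.

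The total effect cannot be estimated, because the documents give no baseline PSA distribution and no rates of long delay or liver events. The doubling times used above are assumptions. No sample-size or precision figure in the plan changes.

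**What to change.** The clinical leads should reconcile three sets of passages. No view is given here on which rule is right.

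1. The synopsis, 7.1.1, 7.8.1 and 9.1.2.2: one end-of-participation rule, saying which kind of progression ends treatment and which ends study follow-up.
2. Sections 7.4 and 7.5: one rule for delays over 10 weeks.
3. Section 7.5 and the Appendix A hepatic footnote: one liver rule, stating which text governs.

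Then write the chosen end-of-participation rule into 11.1.1, 11.1.2.2 and 11.1.2.4, because it fixes the response window and the censoring. State there which PSA progression definition applies, since the size of the PSA-PFS effect turns on it.

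The cost is one amendment with wording changes and no new procedures.
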